9.4.1.1.3 MANAGEMENT OF PROTEINURIA

Regular assessment of proteinuria should be conducted as detailed in the Schedule of Procedures/Assessments ([Table 8](#)). Guidelines for assessment and management of proteinuria:

1. Grading will be based on the 24-hour urinary protein result. Management of lenvatinib administration will be based on the grade of proteinuria according to instructions contained in [Table 2](#), “Dose Modifications for Lenvatinib Treatment-Related Toxicity,”
2. A 24-hour urine collection (within 72 hours) to verify the grade of proteinuria for protein quantitation is required in the following situations:
 - The first (initial) occurrence of $\geq 2+$ proteinuria on urine dipstick while on study drug
 - A subsequent increase in severity of urine dipstick proteinuria occurring on the same lenvatinib dose level
 - When there has been a lenvatinib dose reduction and at the new dose level the urine protein dipstick result is 2+, 3+, or 4+
3. Urine dipstick testing for subjects with proteinuria $\geq 2+$ should be performed on Day 15 (or more frequently as clinically indicated) until the results have been 1+ or negative for 3 consecutive months.

Grading of proteinuria should be performed according to CTCAE v4.03 ([Appendix 3](#)) but will be based on the 24-hour urine collection for total protein result, if a 24-hour urine was performed at that time point.

For subjects with lenvatinib-related toxicity, the dose reduction and/or interruption instructions provided in [Table 2](#) of the study protocol should be followed.

9.4.1.1.4 MANAGEMENT OF HEPATOTOXICITY

Regular monitoring of liver function tests (eg, alanine transaminase [ALT], aspartate transaminase [AST], bilirubin levels) should be conducted as detailed in the Schedule of Procedures/Assessments and as clinically indicated. If signs occur indicating a decrease in liver function by 1 grade or more from baseline, the instructions contained in [Table 2](#) of the protocol should be followed, “Study Treatment Dose Reduction and Interruption Instructions”. Appropriate supportive care should be provided together with close monitoring. If hepatic failure occurs the study drug must be discontinued.

9.4.1.1.5 MANAGEMENT OF THROMBOEMBOLIC EVENTS

Subjects should be advised to pay attention to the symptoms suggestive of venous thromboembolic events, which include acute onset of dyspnea, chest pain, cough, hemoptysis, tachypnea, tachycardia, cyanosis, DVT signs including lower-extremity swelling, redness and warmth to touch or tenderness. In case any of these signs or symptoms appear, subjects should be instructed to report such signs and symptoms promptly to the treating physician. If a thromboembolic event is confirmed, instructions contained in [Table 2](#) of the protocol should be followed, “Study Treatment Dose Reduction and Interruption Instructions.” Appropriate supportive care should be provided together with close monitoring. If a subject experiences life-threatening (Grade 4) thromboembolic reactions, including pulmonary embolism, the study drug must be discontinued.

9.4.1.1.6 MANAGEMENT OF POSTERIOR REVERSIBLE ENCEPHALOPATHY SYNDROME (PRES)

In clinical studies with lenvatinib, events of posterior reversible encephalopathy syndrome (PRES) were reported in less than 1% of lenvatinib-treated subjects. Posterior reversible encephalopathy syndrome is a neurological disorder that can present with headache, seizure, lethargy, confusion, altered mental function, blindness, and other visual or neurological disturbances. Mild to severe hypertension may be present. An MRI is necessary to confirm the diagnosis of PRES. Appropriate measures should be taken to control blood pressure. In subjects with signs or symptoms of PRES, dose interruptions, reductions, or discontinuation may be required per instructions included in [Table 2](#). Please refer to Section 7 of the Investigator's Brochure for further information on lenvatinib, including the full set of special warnings and precautions for use (Section 7.4.4).

9.4.1.1.7 MANAGEMENT OF HYPOCALCEMIA

Serum calcium should be monitored every 3 weeks per the Schedule of Procedures/Assessments. Hypocalcemia should be treated per institutional guidelines (eg, using, as appropriate, calcium, magnesium, and Vitamin D supplementation) until resolution.

9.4.1.1.8 MANAGEMENT OF QT PROLONGATION

Lenvatinib should be withheld in the event of development of QT interval prolongation ≥ 500 msec. Lenvatinib should be resumed at a reduced dose when QTc prolongation is resolved to <480 msec or baseline. Monitor potassium, calcium and magnesium, and replenish as appropriate.

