9.3.2 Exclusion Criteria

1. Prior anticancer treatment within 28 days (or 5 times the half-life, whichever is shorter) or any investigational agent within 30 days prior to the first dose of study drugs. All acute toxicities related to prior treatments must be resolved to Grade ≤ 1 .

2. Subjects must have recovered adequately from any toxicity and/or complications from major surgery prior to starting therapy.
3. Subjects having >1+ proteinuria on urinalysis will undergo 24-hour urine collection for quantitative assessment of proteinuria. Subjects with urine protein ≥ 1 g/24-hour will be ineligible.
4. Gastrointestinal malabsorption, gastrointestinal anastomosis, or any other condition that might affect the absorption of lenvatinib
5. New York Heart Association (NYHA) congestive heart failure of grade II or above, unstable angina, myocardial infarction within the past 6 months, or serious cardiac arrhythmia associated with significant cardiovascular impairment within the past 6 months
6. Prolongation of QTc interval to >480 msec
7. Active hemoptysis (bright red blood of at least 0.5 teaspoon) within 3 weeks prior to the first dose of study drug
8. Active infection (any infection requiring systemic treatment)
9. Subject is known to be positive for Human Immunodeficiency Virus (HIV), Hepatitis B or Hepatitis C
10. Serious nonhealing wound, ulcer, or bone fracture
11. Known intolerance to either of the study drugs (or any of the excipients)
12. History of organ allograft (subject has had an allogenic tissue/solid organ transplant)
13. Biologic response modifiers (eg, granulocyte colony-stimulating factor within 4 weeks before study entry. Chronic erythropoietin therapy is permitted provided that no dose adjustments were made within 2 months before first dose of study treatment.
14. Any medical or other condition which, in the opinion of the investigator, would preclude participation in a clinical study
15. Females who are pregnant or breastfeeding
16. Excluding the primary tumor leading to enrollment in this study, any other active malignancy (except for definitively treated melanoma in-situ, basal or squamous cell carcinoma of the skin, or carcinoma in-situ of the bladder or cervix) within the past 24 months
17. Prior treatment with lenvatinib (no exceptions) or any PD-1, anti-PD-L1, or anti-PD-L2 agent, except:

- the melanoma and NSCLC cohorts, where prior treatment with one anti-PD-1, anti-PD-L1, or anti-PD-L2 agent is allowed.

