9.4.1.1.1 CRITERIA FOR INTERRUPTION OF TREATMENT, DOSE REDUCTION AND RESUMPTION OF TREATMENT

Lenvatinib dose reduction and interruption for subjects who experience lenvatinib-related toxicity will be in accordance with the guidelines provided in Table 2. Once the dose has been reduced, it may not be increased at a later date.

For management of hypertension and proteinuria, refer to main protocol text for instructions before consulting the table below, as appropriate. (See Table 3 for dose reductions. Any dose reduction below 4 mg/day must be discussed with the sponsor. Once the dose has been reduced, it cannot be increased at a later date.) Dose reductions of lenvatinib in Phase 2 occur in succession starting at the RP2D dose identified in Phase 1b.

Table 2 Dose Modifications for Lenvatinib Treatment-Related Toxicity

Lenvatinib Treatment-Related Toxicity ^{a,b}	During Therapy	Adjusted Dose ^f
Grade 1, Tolerable Grade 2		
	Continue treatment	No change
Intolerable Grade 2^{c,d} and Grade 3^g		
First occurrence	Interrupt lenvatinib until resolved to tolerable Grade 2 or Grade 0-1	Reduce lenvatinib by one dose level ^b
Second occurrence (same toxicity or new toxicity)	Interrupt lenvatinib until resolved to tolerable Grade 2 or Grade 0-1	Reduce lenvatinib by one more dose level
Third occurrence (same toxicity or new toxicity)	Interrupt lenvatinib until resolved to tolerable Grade 2 or Grade 0-1	Reduce lenvatinib by one more dose level
Fourth occurrence (same toxicity or new toxicity)	Interrupt lenvatinib until resolved to tolerable Grade 2 or Grade 0-1	Reduce lenvatinib by one more dose level

Grade 4^g: Discontinue lenvatinib
--

- a. An interruption of lenvatinib treatment for more than 21 days (due to lenvatinib treatment-related toxicities) will require a discussion with the sponsor before treatment can be resumed.
- b. Excluding alopecia. Initiate optimal medical management for nausea, vomiting, hypothyroidism, hypertension and/or diarrhea prior to any lenvatinib interruption or dose reduction. For treatment-related hypertension, refer to Management of Hypertension (Section 9.4.1.1.2) for dose modification guidelines.
- c. Applicable only to Grade 2 toxicities judged by subject and/or physician to be intolerable.

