Abnormal laboratory values should not be listed as separate AEs if they are considered to be part of the clinical syndrome that is being reported as an AE. It is the responsibility of the investigator to review all laboratory findings in all subjects and determine if they constitute an AE. Medical and scientific judgment should be exercised in deciding whether an isolated laboratory abnormality should be classified as an AE. Any laboratory abnormality considered to constitute an AE should be reported on the Adverse Event CRF.

Abnormal ECG (QTc) results, if not otherwise considered part of a clinical symptom that is being reported as an AE, should be considered an AE if the QTc interval is more than 450 ms

and there is an increase of more than 60 ms from baseline. Any ECG abnormality that the investigator considers as an AE should be reported as such.

Progression of malignant disease (PD) should not be recorded as an AE in studies where it is included as an endpoint for underlying disease. If the progression leads to an untoward medical occurrence (increased pain, pleural effusion, etc), then this medical occurrence should be the AE.

All AEs must be followed for 30 days after the subject's last dose, or until resolution, whichever comes first. All SAEs must be followed to resolution or, if resolution is unlikely, to stabilization.

Every effort must be made by the investigator to categorize each AE according to its severity and its relationship to the study treatment.

Assessing Severity of Adverse Events

Adverse events will be graded on a 5-point scale according to Common Terminology Criteria for Adverse Event (CTCAE v4.03) ([Appendix 3](#)). Investigators will report CTCAE grades for all AEs (for both increasing and decreasing severity).

Assessing Relationship to Study Treatment

Items to be considered when assessing the relationship of an AE to the study treatment are:

- Temporal relationship of the onset of the event to the initiation of the study treatment
- The course of the event, especially the effect of discontinuation of study treatment or reintroduction of study treatment, as applicable
- Whether the event is known to be associated with the study treatment or with other similar treatments
- The presence of risk factors in the study subject known to increase the occurrence of the event
- The presence of nonstudy, treatment-related factors that are known to be associated with the occurrence of the event

Classification of Causality

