9.5.1.5.6 ELECTROCARDIOGRAMS

Electrocardiograms will be obtained as designated in the Schedule of Procedures/Assessments ([Table 8](#) and [Table 9](#)). Complete, standardized, 12-lead ECG recordings that permit all 12 leads to be displayed on a single page with an accompanying lead II rhythm strip below the customary 3×4 lead format are to be used. In addition to a rhythm strip, a minimum of 3 full complexes should be recorded from each lead simultaneously. Subjects must be in the recumbent position or sitting for a period of 5 minutes prior to the ECG. The Fridericia correction method for calculating QTc will be used.

An ECG abnormality may meet the criteria of an AE as described in this protocol (see [Section 9.5.1.5.1](#)) and the CCGs. In these instances, the AE corresponding to the ECG abnormality will be recorded on the Adverse Events CRF.

QT prolongation has been seen in some lenvatinib studies. Monitor electrocardiograms every cycle (as specified in the Schedule of Assessments) in patients with congenital long QT syndrome, congestive heart failure, bradyarrhythmias, or those who are taking drugs known to prolong the QT interval, including Class Ia and III antiarrhythmics. Refer to the Lenvatinib package insert.

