 - d. Assessments will include vital signs (resting BP, HR, RR, and body temperature), weight, and height. Height will be measured at the Screening Visit only. Elevated BP assessment (ie, systolic BP ≥ 140 mmHg or diastolic BP ≥ 90 mmHg) should be confirmed by a repeat assessment after a minimum of 1 hour. One BP assessment is defined as the mean value of 3 measurements at least 5 minutes apart. Subjects with systolic BP ≥ 160 mmHg or diastolic BP ≥ 100 mmHg must have their BP monitored every 2 weeks (on Day 1 and Day 15 or more frequently, as clinically indicated) until systolic BP has been ≤ 150 mmHg and diastolic BP has been ≤ 95 mmHg for 3 consecutive months. If a new event of systolic BP ≥ 160 mmHg or diastolic BP ≥ 100 mmHg occurs, the subject must resume the Day 15 evaluation until systolic BP has been ≤ 150 mmHg and diastolic BP has been ≤ 95 mmHg for 3 consecutive months. As of Amendment 09, weight and body temperature will be assessed as clinically indicated in the Extension Phase.
 - e. A physical examination will be performed at the Screening or Baseline Visit, on C1D15, on D1 of each subsequent cycle, and at the Off-Tx Visit assessment. A symptom-directed physical examination will be performed on C1D1 and at any time during the study, as clinically indicated. As of Amendment 09, oral examination will be included
 - f. Required if screening physical examination was performed >7 days prior to C1D1.
 - g. Single, 12-lead ECG. Subjects must be in the recumbent position for a period of 5 min prior to the ECG. During the Treatment and Extension Phases, ECGs will be collected every cycle.
 - h. Phone contact will take place on Day 8 (± 2 days) of C1 to assess subjects for development of early toxicity. An unscheduled visit will occur prior to C1D15 if deemed necessary by the investigator.
 - i. Clinical laboratory tests will be performed by the local laboratory. Assessments should be performed within 72 h prior to the visit. Clinical chemistry and hematology results must be reviewed prior to administration of study drug on C1D1 and within 48 hours after receiving quick estimation. If there is \geq Grade 3 clinical significant hematologic or clinical chemistry toxicity, repeat laboratory test and AEs assessment at least every 7 days (until improvement to $<$ Grade 3). Thyroid function will be assessed every 2 Cycles (C3D1, C5D1, etc.).

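### The lenvatinib hold in Protocol 9.4.1.1.8 is set on QT but resumption is on QTc, so above 60 bpm a QTcF of 500 msec need not trigger the hold

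*Protocol*

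**What the plan says.** Protocol 9.4.1.1.8, added in Amendment 09, gives the dosing rule in two consecutive sentences. The first reads "Lenvatinib should be withheld in the event of development of QT interval prolongation", with a threshold of 500 msec or more. The second reads "Lenvatinib should be resumed at a reduced dose when QTc prolongation is resolved" to below 480 msec or to baseline.

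Elsewhere the documents keep the two measures apart:

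- The Protocol abbreviation list (section 4) has separate entries for QT, the measured interval, and QTc, the calculated value.
- SAP 5.6.6 summarises QT, QTcB and QTcF as separate ECG parameters.
- Exclusion criterion 6 (Protocol 9.3.2) is on the corrected scale: "Prolongation of QTc interval to >480 msec".
- The ECG adverse event rule (Protocol 9.5.1.5.1) is also on QTc. It requires a value above 450 ms "and there is an increase of more than 60 ms from baseline".
- Protocol 9.5.1.5.6 names the correction: "The Fridericia correction method for calculating QTc will be used".

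No section states that QT in the hold sentence means QTc.

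**The concern.** This is a numeric stop rule for patient safety, and its trigger and release are on different scales. Because QTc exceeds QT at heart rates above 60 bpm, a site that applies 500 msec to the measured interval will hold lenvatinib later than a site that applies it to QTcF. A patient with a QTcF of exactly 500 msec and a heart rate above 60 bpm would not meet this section's hold.

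The delay could last. Table 9, footnote g, states: "During the Treatment and Extension Phases, ECGs will be collected every cycle". With 21-day cycles, a hold not triggered on one scheduled ECG may not be looked at again for about three weeks. The protocol itself notes that QT prolongation has occurred in lenvatinib studies (9.5.1.5.6).

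**Working it through.** The plan gives no figure of its own to reproduce here. The check converts between the two scales.

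**Inputs**

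- Hold threshold: QT of 500 msec or more (Protocol 9.4.1.1.8).
- Resumption threshold: QTc below 480 msec, or baseline (same section).
- Correction: Fridericia (Protocol 9.5.1.5.6).
- Adverse event rule: QTc above 450 ms and a rise of more than 60 ms (Protocol 9.5.1.5.1).
- Highest eligible QTc: 480 msec (exclusion criterion 6).
- Heart rates: assumed, 65 to 100 bpm. The documents give none.

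**Formula.** QTcF = QT / (60/HR)^(1/3). At 60 bpm the divisor is 1, so the scales coincide. At any faster rate QTcF is larger than QT.

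**Example at 80 bpm.** RR = 60/80 = 0.75 s, and its cube root is 0.9086. A QT of 500 is a QTcF of 500/0.9086 = 550.3. A QTcF of 500 is a QT of 500 × 0.9086 = 454.3.

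| HR (bpm) | QTcF when QT = 500 | QT when QTcF = 500 | Width of QTcF range from 500 upward that is not held (ms) |
|---|---|---|---|
| 60 | 500.0 | 500.0 | 0 |
| 65 | 513.5 | 486.8 | 14 |
| 70 | 526.4 | 475.0 | 26 |
| 80 | 550.3 | 454.3 | 50 |
| 90 | 572.4 | 436.8 | 72 |
| 100 | 592.8 | 421.7 | 93 |

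**Does the adverse event rule catch a QTcF of 500?**

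- Baseline 440: the rise is 500 − 440 = 60, which is not more than 60, so the rule is not met.
- Baseline 460: the rise is 40, not met.
- Baseline 480: the rise is 20, not met. The rule then needs QTc above 480 + 60 = 540.
- Baseline below 440: the rise exceeds 60, so the rule is met.

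Meeting the rule makes the finding an adverse event. It does not by itself order a hold.

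**Slow rates.** A QT of 500 equals a QTcF of 480 at 60 × (480/500)^3 = 53.1 bpm. Below that rate a narrow band meets the hold and resumption thresholds together. At 50 bpm a QTcF of 480 is a QT of 510.1, so the band is QT 500 to 510. This inconsistency errs towards caution.

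**The case against.** The best reply is that no physician would apply the rule literally. The two sentences describe one event, and the second calls it QTc prolongation. The protocol also uses QT prolongation as the general name of the condition, and every other numeric limit is on QTc. On this view it is a typing slip with one sensible reading. That is probably what was meant, and it makes the correction uncontroversial. It does not change the number that a site reads in the rule.

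The second reply is Table 2. Section 9.4.1.1.1 says that lenvatinib reduction and interruption for related toxicity "will be in accordance with the guidelines provided in Table 2", so Grade 3 or intolerable Grade 2 toxicity may stop dosing whatever 9.4.1.1.8 says. This stands in part. It depends on attribution and grading, and the QTc grade cut-offs are not in the documents, so its effect at a QTcF of 500 cannot be verified. Section 9.4.1.1.8 does not point to Table 2, whereas the section on posterior reversible encephalopathy syndrome says dose changes "may be required per instructions included in" that table. Little weight should rest on this contrast, because the hypocalcemia and jaw osteonecrosis sections have no pointer either.

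Third, the adverse event rule does catch a QTcF of 500 when baseline is below 440, and an investigator may report or act on any ECG abnormality. Both are true. The distribution of baseline QTc is not given, so the share of subjects left uncovered is unknown.

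Fourth, reach is limited. The text dates from Amendment 09, and subjects who stop pembrolizumab move to commercial lenvatinib where local rules allow (Protocol 9.1). The number still on study lenvatinib is not stated and may be small.

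**Conclusion.** The concern holds. As written, the hold threshold is on a different scale from the resumption threshold and from the protocol's other QTc limits. Above 60 bpm it does not require a hold at a QTcF of 500 msec. The size depends on heart rate: the range not held is 14 ms wide at 65 bpm, 50 ms at 80 bpm and 93 ms at 100 bpm. The heart rates are assumptions, but the direction is the same at every rate above 60 bpm.

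The conclusion is confined to this section's own trigger. It does not claim that a patient would necessarily continue dosing, because Table 2 and investigator judgement remain. No endpoint, sample size, power or alpha figure is affected. The correction should be made because this is a safety threshold and should not depend on each site inferring a missing letter.

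**What to change.** In Protocol 9.4.1.1.8, set the hold at a QTc (Fridericia) of 500 msec or more, and set resumption at a QTcF below 480 msec or baseline. Tell sites by letter.

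The cost is one term in each of two sentences, plus the letter. The same ECGs and the correction already named in 9.5.1.5.6 are used, so no procedure or visit is added.

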9.4.1.1.9 MANAGEMENT OF OSTEONECROSIS OF THE JAW

Perform an oral examination prior to treatment with lenvatinib and periodically during lenvatinib treatment. Advise participants regarding good oral hygiene practices. Avoid invasive dental procedures, if possible, while on lenvatinib treatment, particularly in participants at higher risk. For participants requiring invasive dental procedures, discontinuation of bisphosphonate treatment may reduce the risk of osteonecrosis of the jaw (ONJ). Withhold lenvatinib if ONJ develops and restart based on clinical judgement of adequate resolution.

9.4.1.2 Pembrolizumab

Pembrolizumab (200 mg) will be administered as a 30-minute IV infusion, Q3W (infusions lasting between 25 minutes to 40 minutes are acceptable). The Pharmacy Manual contains specific instructions for the preparation of the pembrolizumab infusion and administration of infusion solution.

Subjects should maintain a normal diet unless modifications are required to manage an AE such as diarrhea, nausea or vomiting.

Study treatment with pembrolizumab may be administered up to 3 days before or after the scheduled D1 of each cycle due to administrative reasons.

Adverse events (both nonserious and serious) associated with pembrolizumab exposure may represent an immunologic etiology. These AEs may occur shortly after the first dose or several months after the last dose of treatment. Pembrolizumab must be withheld for drug-related toxicities and severe or life-threatening AEs as per [Table 4](#) below. See [Section 9.4.1.2.1](#) for supportive care guidelines, including use of corticosteroids.

Table 4 Dose Modification and Toxicity Management Guidelines for Immune-related Adverse Events Associated with Pembrolizumab

Immune-related Adverse Event	Toxicity Grade (CTCAE v4.0)	Action with Pembrolizumab	Corticosteroids and/or Other Therapies	Monitoring and Follow-up

General instructions:
 
 Severe and life-threatening irAEs should be treated with IV corticosteroids followed by oral steroids. Other immunosuppressive treatment should begin if the irAEs are not controlled by corticosteroids. Pembrolizumab must be permanently discontinued if the irAE does not resolve or the corticosteroid dose is not ≤ 10 mg/day within 12 weeks of the last pembrolizumab-treatment. The corticosteroid taper should begin when the irAE is \leq Grade 1 and continue at least 4 weeks. 
If pembrolizumab has been withheld, pembrolizumab may resume after the irAE decreased to \leq Grade 1 after corticosteroid taper.
				
Pneumonitis	Grade 2	Withhold	Administer corticosteroids (initial dose of 1 to 2 mg/kg prednisone or equivalent) followed by taper. Add prophylactic antibiotics for opportunistic infections.	Monitor participants for signs and symptoms of pneumonitis. Evaluate participants with suspected pneumonitis with radiographic imaging and initiate corticosteroid treatment.
	Recurrent Grade 2, 3 or 4	Permanently discontinue		
Diarrhea / Colitis	Grade 2 or 3	Withhold	Administer corticosteroids (initial dose of 1 to 2 mg/kg prednisone or equivalent) followed by taper.	
Monitor participants for signs and symptoms of enterocolitis (ie, diarrhea, abdominal pain, blood or mucus in stool with or without fever) and of bowel perforation (ie, peritoneal signs and ileus).
 
Participants with \geq Grade 2 diarrhea suspecting colitis should consider GI consultation and performing endoscopy to rule out colitis.
 
Participants with diarrhea/colitis should be advised to drink liberal quantities of clear fluids. If sufficient oral fluid intake is not feasible, fluid and electrolytes should be substituted via IV infusion.

	Recurrent Grade 3 or Grade 4	Permanently discontinue		

Table 4 Dose Modification and Toxicity Management Guidelines for Immune-related Adverse Events Associated with Pembrolizumab

Immune-related Adverse Event	Toxicity Grade (CTCAE v4.0)	Action with Pembrolizumab	Corticosteroids and/or Other Therapies	Monitoring and Follow-up
AST or ALT elevation or Increased Bilirubin	Grade 2	Withhold	Administer corticosteroids (initial dose of 0.5 to 1 mg/kg prednisone or equivalent) followed by taper. Administer corticosteroids (initial dose of 1 to 2 mg/kg prednisone or equivalent) followed by taper.	Monitor with liver function tests (consider weekly or more frequently until liver enzyme value returned to baseline or is stable).
	Grade 3 or 4	Permanently discontinue		
Type 1 diabetes mellitus (T1DM) or Hyperglycemia	Newly onset T1DM or Grade 3 or 4 hyperglycemia associated with evidence of β -cell failure	Withhold ^a	Initiate insulin replacement therapy for participants with T1DM. Administer anti-hyperglycemic in participants with hyperglycemia.	Monitor participants for hyperglycemia or other signs and symptoms of diabetes.
Hypophysitis	Grade 2	Withhold	Administer corticosteroids and initiate hormonal replacements as clinically indicated	Monitor for signs and symptoms of hypophysitis (including hypopituitarism and adrenal insufficiency).
	Grade 3 or 4	Withhold or permanently discontinue		
Hyperthyroidism	Grade 2	Continue	Treat with nonselective beta-blockers (eg, propranolol) or thionamides as appropriate	Monitor for signs and symptoms of thyroid disorders.
	Grade 3 or 4	Withhold or permanently discontinue		
Hypothyroidism	Grade 2, 3 or 4	Continue	Initiate thyroid replacement hormones (eg, levothyroxine or liothyronine) per standard of care	Monitor for signs and symptoms of thyroid disorders.
Nephritis: grading according to increased creatinine	Grade 2	Withhold	Administer corticosteroids (prednisone 1 to 2 mg/kg or equivalent) followed by taper	Monitor changes of renal function.
	Grade 3 or 4	Permanently discontinue		

Table 4 Dose Modification and Toxicity Management Guidelines for Immune-related Adverse Events Associated with Pembrolizumab

Immune-related Adverse Event	Toxicity Grade (CTCAE v4.0)	Action with Pembrolizumab	Corticosteroids and/or Other Therapies	Monitoring and Follow-up
or acute kidney injury.				
Myocarditis	Grade 1	Withhold	Based on severity of AE administer corticosteroids	Ensure adequate evaluation to confirm etiology and/or exclude other causes.
	Grade 2, 3 or 4	Permanently discontinue		
All other immune-related AEs	Persistent Grade 2	Withhold	Based on severity of AE administer corticosteroids	Ensure adequate evaluation to confirm etiology or exclude other causes.
	Grade 3	Withhold or discontinue based on event ^b .		
	Recurrent Grade 3 or Grade 4	Permanently discontinue		

AE(s) = adverse event(s), ALT = alanine aminotransferase, AST = aspartate aminotransferase, CTCAE = Common Terminology Criteria for Adverse Events, DRESS = Drug Rash with Eosinophilia and Systemic Symptom; GI = gastrointestinal, IO=immuno-oncology; irAE = immune-related adverse event, IV = intravenous, SJS = Stevens-Johnson Syndrome; T1DM = Type 1 diabetes mellitus; TEN = Toxic Epidermal Necrolysis; ULN = upper limit of normal.

Note: Non-irAE will be managed as appropriate, following clinical practice recommendations.

^a The decision to withhold or permanently discontinue pembrolizumab is at the discretion of the investigator or treating physician. If control achieved or \leq Grade 2, pembrolizumab may be resumed.

^b Events that require discontinuation include, but are not limited to: Guillain-Barre Syndrome, encephalitis, myelitis, DRESS, SJS, TEN and other clinically important irAEs (eg, vasculitis and sclerosing cholangitis).

Dosing interruptions are permitted in the case of medical/surgical events or logistical reasons not related to study therapy (eg, elective surgery, unrelated medical events, subject vacation, and/or holidays). Subjects should be placed back on study treatment within 3 weeks of the scheduled interruption, unless otherwise discussed with the sponsor. The reason for interruption should be documented in the subject's study record.

